# **Sample Size**

To have 80% power to compare a 95% pick-up rate in more cellular slides with an 80% pick-up rate in less cellular slides would require 90 slides in each bands of cellularity. Power will be increased by each slide being read by three reviewers. This can be estimated by applying a cluster sampling correction. If the agreement between reviews has a kappa coefficient of 0.75, power will increase to 87%. In total 1,440 slides would be required for each system (720 high grade / 720 mild moderate). A further 960 cases will be included of similar cellularity. These estimates ignore the matching of slides across bands. If this matching of slides can be incorporated in the statistical analysis, power will increase slightly.

# **Statistical Analysis**

A logistic random effects model with variance terms for slide and source will be used to model pick-up rate for high and low grade abnormalities including covariates for cellularity and diagnostic sub-type. This will be used to estimate the levels of cellularity at which pick-up rate decreases. It is likely that inter-review agreement will change according to cellularity. This will be investigated by estimating the kappa coefficient according to bands of cellularity and by including random coefficient terms into the logistic random effects model.

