# **Relevance to Commissioning Brief:**

This proposal addresses all aspects of the commissioning brief as follows:

- Current working practice in a large number of laboratories throughout England, Scotland and Wales will be surveyed to determine what minimum cellularity levels are currently being used to assess whether an LBC sample is adequate.
- The reasons for the choice of minimum cellularity by these laboratories will be examined.
- A comparison of declared and actual practice will provide evidence of how closely laboratories adhere to these local guidelines.
- In the second part of the study, multiple slides will be prepared from individual samples to assess the impact of overall cellularity; relative proportion of abnormal cells; and the type and presentation of abnormal cells on the ability of primary screeners to routinely detect those abnormalities.
- This will provide an estimate of the level of cellularity at which a satisfactory pick-up rate of high and low grade disease can be detected
- It will also allow the estimation of a level of cellularity which minimises samples being wrongly labelled 'negative' when they are inadequate.
- The study will compare both of the current LBC platforms and will assess any operational differences relating to cell counting.
- The study will establish a reliable method of determining the total cellularity for both current LBC systems.
- The use of transformation zone indicators as a quality indicator of smear taker practice will also be examined.

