# **Objectives:**

- To assess current standards and practice for the reporting of LBC preparations across England, Scotland and Wales
- To determine the cellularity of samples deemed inadequate, negative or abnormal by a range of laboratories across the country.
- To determine the cellularity of samples deemed negative, HPV+ in the ARTISTIC/MCM trial.
- To assess the impact of varying the overall cellularity; relative proportion of abnormal cells and the type and presentation of dyskaryotic cells on their likelihood of detection.
- To determine the threshold of cellularity of LBC preparations which allow the majority of samples containing abnormal cells to be detected by routine screening.
- To establish a reproducible method for rapidly estimating the cellularity of an LBC sample.

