Eight preparations will be made from each sample. Serial dilutions with approximate cellularities of 5-10k, 10-15k, 15-20k, 20-25k, 25-35k, 35-45k, 45-55k and 55+k will be made from half of the cases. The range of dilutions is skewed towards preparations of lower cellularity as these are expected to have higher false negative rates. The remaining cases will be mixed with known negative cases in varying proportion to establish sets of slides containing <25, 25-49, 50-99, 100-149, 150-199, 200-399, 400-799, 800-1600 and 1600+abnormal cells. In total 3,000 new slides will be prepared.

Each of the prepared slides will be assessed by two members of a four panel expert cytology group (to include [name]). Each slide will have a total cell count and a total abnormal cell count performed by the two panel members. Cases in which there is a variation of >10% between either of these counts will be assessed by at least three panel members on a multi-headed discussion microscope and a consensus decision reached.

The prepared slides will then be block randomised with 1,000 negative and 1,000 inadequate cases (total of 2,000) of similar cellularities in a ratio of 3:2 to minimise screener outcome bias.

Determination of "true" negative is always a problematic area in cervical cytology. In order to address this the Team proposes a modification to the existing protocol whereby 200 of the 1,000 negative slides will derive from confirmed HPV-ve cases. 100 of these HPV-ve slides will be acquired from archived material from the ARTISTIC/MCM trial. As the ARTISTIC/MCM trial used only Thin Prep® cases, these will be matched by newly acquired HPV-ve material from the SurePath™ system. It is estimated that 150 HPV tests will be required to obtain a cohort of HPV-ve, Cytology-ve cases.

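### The Part 2 model names neither abnormal-cell count nor the dilution/mixing series, although half the prepared cases are built to vary that count

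*Protocol*

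**What the plan says.** The Part 2 Statistical Analysis section specifies "A logistic random effects model with variance terms for slide and source" and uses it to "model pick-up rate for high and low grade abnormalities including covariates for cellularity and diagnostic sub-type". Of this model it says: "This will be used to estimate the levels of cellularity at which pick-up rate decreases". That level of cellularity is the stated Part 2 outcome.

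The Part 2 Design section makes two series of slides.
- **Dilution series.** Eight preparations in total-cellularity bands from 5-10k to 55+k "will be made from half of the cases".
- **Mixing series.** "The remaining cases will be mixed with known negative cases in varying proportion", giving slides from under 25 to over 1,600 abnormal cells. The introduction to Part 2 says that background cellularity is kept similar in these preparations, without giving a value.

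Both quantities are measured: "Each slide will have a total cell count and a total abnormal cell count performed by the two panel members". The Objectives include the impact of overall cellularity, "relative proportion of abnormal cells and the type and presentation of dyskaryotic cells on their likelihood of detection". The commissioning-brief section and the project summary repeat this aim. The Part 2 introduction also cites a case-control study in which abnormal-cell number was the strongest discriminator of false negatives, with odds 23.7 times greater below 50 cells than at 200 or more.

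**The concern.** The two series do different things. Diluting a case moves total and abnormal cells down together. Mixing moves abnormal cells while total cells stay roughly still. Their effects can be separated only if the analysis knows the abnormal-cell count or the series a slide came from, and the named model has neither.

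Two consequences follow. First, if all abnormal slides enter one fit on cellularity, the mixing slides contribute large variation in pick-up at nearly constant cellularity. They shift and flatten the curve from which the threshold is read. Second, the objective on abnormal cells has no stated analysis, although half the cases are prepared for it.

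The other named terms do not fill the gap. Sub-type, including the scanty-cell type in the Design section, describes the source case and is the same for all eight of its preparations. Random intercepts for slide and source absorb variation but do not estimate this effect, and abnormal count varies within a case in both series.

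**Working it through.** **1. Layout, and the protocol's own figures.**
- Slides: 180 + 180 = 360 cases, × 8 preparations = 2,880 (the protocol rounds to 3,000). Half is 180 × 8 = 1,440 slides in each series.
- Slides per band: for 95% v 80% at 80% power, with two-sided 5% assumed because alpha is not stated, the two-proportion formula gives 76, or 88 with continuity correction. The protocol states 90.
- Three reads at kappa 0.75: effective n = 90 × 3 / (1 + 2 × 0.75) = 108, with continuity-corrected power 88.5%. The protocol states 87%.
- Per system: 8 bands × 90 × 2 grades = 1,440 = 180 × 8, as stated.

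The sizing therefore reproduces, but it counts every case as if it were diluted.

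**2. What each fit estimates.** Suppose logit(pick-up) = a + b·log2(abnormal count) + g·log2(cellularity). Within a diluted case the abnormal fraction is fixed, so the slope on log2(cellularity) is b + g. Within a mixed case cellularity hardly moves, so pick-up varies through b alone. A pooled fit on cellularity alone estimates neither b + g nor g.

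**3. Illustrative simulation.** None of these effect sizes is in the protocol.
- Layout: 360 cases × 8 slides × 3 reads, half diluted and half mixed.
- logit = 2.0 + b·log2(A/100) + g·log2(C/20k) + case and slide effects (SD 0.7 each).
- Dilution series: band midpoints 7.5k to 65k; abnormal fraction median 1%, log SD 1.
- Mixing series: A = 12, 37, 75, 125, 175, 300, 600, 1,200, at a background of 20k or 50k (log SD 0.15).
- Fits: ordinary logistic regression, with random effects simulated but not fitted. Figures are medians of 60 runs.

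| b | g | Mixing background | Slope, dilution only | Slope, pooled | Slope, pooled, adjusted for count and system | 90% pick-up, dilution only | 90% pick-up, pooled |
|---|---|---|---|---|---|---|---|
| 0.5 | 0.3 | 20k | 0.69 | 0.63 | 0.27 | 24k | 30k |
| 0.5 | 0.3 | 50k | 0.67 | 0.36 | 0.26 | 24k | 46k |
| 0.5 | 0 | 20k | 0.43 | 0.41 | 0.01 | 27k | 38k |
| 0.5 | 0 | 50k | 0.42 | 0.10 | 0.00 | 27k | beyond range |
| 0.8 | 0 | 20k | 0.63 | 0.56 | -0.01 | 22k | 34k |
| 0.8 | 0 | 50k | 0.65 | 0.12 | 0.01 | 23k | beyond range |
| 0.8 | 0.3 | 20k | 0.88 | 0.75 | 0.27 | 22k | 30k |
| 0.8 | 0.3 | 50k | 0.87 | 0.35 | 0.27 | 22k | 56k |

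With an added system effect of 0.6 (b = 0.5, g = 0.3), the dilution-only figure is 19k. The pooled figure is 24k (20k background) or 30k (50k background). The system effect is recovered at 0.54 when system is in the model.

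**4. Sensitivity.** A cruder calculation uses the cited odds ratio, placed between 25 and 300 cells: slope per log cell = ln(23.7)/ln(12) = 1.27, with 95% pick-up at 300 cells. At 25-35k, dilution pick-up is 0.91 and the mixing mean is about 0.81. If all mixing slides sit in that band, the pooled rate is (180 × 0.914 + 1,440 × 0.812)/1,620 = 0.82, about 9 points lower. Varying the abnormal fraction (0.5-3%) and its log SD (0.5-1.5) moves this gap from about nil to 16 points.

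**The case against.** Four objections have force.

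- **The covariate list is not closed.** The text says that the model includes these covariates. A reader might infer that abnormal-cell count is excluded; the wording does not go that far. The section is still incomplete on a factor that the design is built around.
- **A pooled fit is not stated.** The model's stated purpose, finding where pick-up falls with cellularity, is the dilution series' question. Fitted to that series alone, cellularity unadjusted for abnormal count is arguably the right quantity, because a sparse sample loses abnormal cells along with the rest. Adjusting for count moves the slope towards the direct effect of cellularity (the adjusted column above), which is not the adequacy threshold. This stands, and it shapes the fix. But the section does not restrict the fit to one series.
- **A local dip in the curve is not shown.** A reader might infer from the 9-point figure that pick-up would fall falsely at one cellularity. That needs all 1,440 mixing slides in one band, which the protocol does not say, and a logistic model with a single slope cannot dip. With mixing backgrounds spread evenly over the eight bands, the pooled rates rise steadily from 0.76 to 0.89: lower and flatter, but with no dip. The odds ratio also comes from conventional smears, as the protocol itself cautions.
- **LBC system.** It is named in the Part 1 model and not here, so a reader might infer that the promise "The study will compare both of the current LBC platforms" goes unanswered. The protocol does not support that. Part 2 is sized for each system, which fits separate analyses, and the aim is partly served by the Part 1 model and the cell-counting sub-study. What remains is a clarification.

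**Conclusion.** The point holds as a mismatch between the Part 2 model and the Part 2 design. The factor deliberately varied in half the prepared cases is measured on every slide and named as an objective, but it is not in the named model. Nor does the protocol say how the two series are combined. The objective on abnormal cells therefore has no stated analysis, whichever way the threshold is fitted.

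The bias in the threshold is conditional on a pooled fit, and no single size can be given. In every simulated setting pooling raised the cellularity for 90% pick-up, by roughly 5-12k with a 20k background and by more with a 50k background. The cruder calculation shows that the gap can also be about nil. The result rests on the assumed effects, the assumed abnormal fraction and the unstated mixing background. Shifts of this order matter when the thresholds in use, per the Background section, are 5,000 and 15,000 cells. No data are lost, so the matter can be settled at any time before analysis.

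**What to change.** In the Part 2 Statistical Analysis section, state that:

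1. The cellularity threshold is estimated from the dilution series, or from a joint model with the threshold read at a stated abnormal-cell fraction.
2. The abnormal-cell effect is estimated with log abnormal-cell count (or proportion) as a covariate, using the mixing series or a joint model with a series indicator.
3. Part 2 is fitted separately by LBC system, or with LBC system as a covariate, in line with the per-system sizing.

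This is a change of wording. All the variables are already collected, and a joint model needs only a few more parameters.

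The cost to weigh is precision. The dilution series has 90 cases per system. With grades split evenly that is 45 slides per band, grade and system, not 90. Three reads at kappa 0.75 give an effective 45 × 3 / 2.5 = 54, and power for the protocol's 95% v 80% comparison of two bands is then 54% (continuity-corrected) to 66% (uncorrected). A regression over all eight bands uses more of the data than that pairwise comparison. The sample-size text should nevertheless say which slides inform the threshold.

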#### **Outcome Measures**

Outcomes will include an estimate of the level of cellularity at which a satisfactory pick-up rate of high and low grade disease can be detected.

# **Trial Supervision**

There will be a Study Management Group (SMC) consisting of applicants, which will meet monthly. An appropriately constituted Trial Steering Group (TSG) with an independent chair will be convened as soon as possible after the grant is awarded. The TSG will meet twice a year. There will be a Data Monitoring and Ethics Committee (DMEC) which will be independent of the applicants and of the TSC.

# **Project Milestones**

| Months into project                 | 0-3 | 3-6 | 6-9 | 9-12 | 12-15 | 15-18 |
|-------------------------------------|-----|-----|-----|------|-------|-------|
|                                     |     |     |     |      |       |       |
| Set up phase                        |     |     |     |      |       |       |
| Recruit staff                       |     |     |     |      |       |       |
| Staff training                      |     |     |     |      |       |       |
| Formulate database                  |     |     |     |      |       |       |
| Ethics approval for part 2          |     |     |     |      |       |       |
|                                     |     |     |     |      |       |       |
| Part 1                              |     |     |     |      |       |       |
| Development of questionnaire        |     |     |     |      |       |       |
| Questionnaire completed & returned  |     |     |     |      |       |       |
| Slides gathered & submitted to labs |     |     |     |      |       |       |
| Slides counted & returned to SMC    |     |     |     |      |       |       |
|                                     |     |     |     |      |       |       |
| Part 2                              |     |     |     |      |       |       |
| Preparation of new slides sets      |     |     |     |      |       |       |
| Evaluation of new slide sets        |     |     |     |      |       |       |
| Slide sets submitted to labs        |     |     |     |      |       |       |

| Slide circulation complete |  |  |  |
|----------------------------|--|--|--|
|                            |  |  |  |
| Analysis of data           |  |  |  |
|                            |  |  |  |
| Report writing             |  |  |  |
|                            |  |  |  |

# **Summary of Project:**

The first part of the study surveys current working practice to establish both the declared laboratory thresholds for LBC specimen adequacy and those thresholds which are operating in practice, with a view to determining the respective levels of each and whether they are different.

It also establishes cohorts of inadequate, negative and abnormal cases which have been reported in a routine screening setting for which total cell counts are known. This information will supplement that from part 2 and will provide an estimate of screening sensitivity at different levels of cellularity.

The second part of the study will assess the contribution of differing total cellularity; relative proportion of abnormal: normal cells; and dyskaryotic sub-type on the likelihood that the slide will be categorised as abnormal. Slide sets comprising serial dilutions of known abnormal cases and of preparations with varying ratios of dyskaryotic to total squamous cells will be assessed by independent review panels. The results will allow an estimate of a level of cellularity at which most abnormalities are likely to be detected and will provide an evidence base to inform national guidance relating to the minimum acceptable cellularity for a cervical LBC sample.

# **Summary in Plain English:**

Liquid Based Cytology (LBC) was approved as the recommended method for preparing cervical samples in 2003. National pilot studies showed that this method was superior to conventional spread smears and reduced the inadequate rate from 10% to 1-2%. However, the number of cells required for these samples to be deemed adequate remains the subject of debate. There is a risk that samples may be described as negative when they are really inadequate and that abnormalities could therefore be missed.

An adequate LBC sample is one in which sufficient numbers of cells are present to allow the detection of an abnormality were it to be present. This study aims to establish the threshold of cellularity which will minimise the risk of false negative reports.

The first part of the study surveys current practice in laboratories throughout mainland UK using LBC for cervical screening and establishes the cellularity of a large cohort of inadequate, negative and abnormal slides. The second part of the study evaluates the ability of screeners to detect abnormalities of differing type and relative abundance. This will be done by preparing sets of slides which vary in their total cellularity and in the total number, type and relative proportion of abnormal cells. These will be presented to a large number of laboratories for independent evaluation. The results will allow an estimate of a level of cellularity at which most abnormalities are likely to be detected and will hence determine a safe minimum cellularity.

This study is led by a team of international and national experts with many years of experience in cervical screening, liquid based cytology and the conduct and evaluation of clinical trials.

